7.1.1. Liver Chemistry Monitoring and Stopping Criteria

Liver chemistry stopping, and increased monitoring criteria have been designed to assure participant safety and to evaluate liver event etiology. Study intervention will be discontinued for a participant if the liver stopping criteria are met.

Discontinuation of study intervention for abnormal liver tests is required when:

- a participant meets one of the conditions outlined in [Table 7](#).
- when in the presence of abnormal liver chemistries not meeting protocol-specified stopping rules, the investigator believes study intervention discontinuation is in the best interest of the participant.

[Table 7](#) lists the criteria for withholding or discontinuing the study medication in a study participant with elevation of ALT. Additional testing will be performed (see safety follow-up procedures for participants who meet increased monitoring or stopping criteria), and the participant monitored until liver chemistry abnormalities resolve, stabilize, or return to within baseline values. The participant must then attend the follow-up visits specified in the SoA.

Every attempt must be made to have the participant evaluated (within 24 hours) for repeat assessment of liver chemistries and additional testing and close monitoring (a specialist or hepatology consultation is recommended). Participants must be monitored weekly until liver chemistry abnormalities (ALT, AST, alkaline phosphatase, bilirubin) resolve, stabilize, or return to within baseline values. Upon completion of the safety follow-up procedures (see below), the participant must attend the follow-up visits specified in the SoA.

Table 7 Liver Chemistry Monitoring and Stopping Criteria

ALT Level	Monitoring Plan	Discontinuation
10x ULN ≤ ALT <12x ULN and Bilirubin ≤1.5x ULN and INR ≤1.5 (if available)	Monitor twice weekly Additional lab assessments	Permanently discontinue IMP if ALT >10x ULN >4 weeks
ALT ≥12x ULN and Bilirubin≤1.5x ULN and INR ≤1.5 (if available)	Hold dose Monitor twice weekly Additional lab assessments if not already done Take off hold: 150 mg SC weekly when ALT <10x ULN; increasing dose to 300 mg (if applicable) should be agreed with Medical Monitor	Permanently discontinue IMP if any of the following apply: 
 • ALT ≥10x ULN >4 weeks • ALT ≥12x ULN recurs after IMP taken off hold
ALT ≥3x ULN and 1.5x ULN <bilirubin ≤2x ULN (>35% direct) and INR ≤1.5 (if available)	Hold dose Monitor twice weekly Additional lab assessments if not already done Take off hold: 150 mg SC weekly when bilirubin returns to <1.5x ULN; increasing dose to 300 mg (if applicable) should be agreed with Medical Monitor	Permanently discontinue IMP if the following recurs after IMP taken off hold: 1.5x ULN <bilirubin ≤2x ULN (>35% direct) And INR ≤1.5 (if available)
ALT ≥3x ULN and any of the following apply: 
 • bilirubin >2x ULN (>35% direct) • associated with the appearance or worsening of hepatitis symptoms • INR >1.5 (if available) 		Permanently discontinue IMP Monitor twice weekly until stable ALT Additional lab assessments if not already done

ALT = alanine aminotransferase; IMP = investigational medicinal product; ULN = upper limit of normal

*Notes:

- Any abnormal laboratory parameters that meet the criteria for individual treatment discontinuation must be confirmed by retest of a new collection of blood samples as soon as possible.

- Any clinically significant deterioration from the baseline in the liver parameters must be confirmed by retesting ALT, total bilirubin, direct bilirubin, and INR (if available).
- If one criterion in the list above is met and confirmed by retesting, further treatment may be discontinued for this participant after discussion with the Medical Monitor. Results of retesting must be evaluated before the next dose is administered.
- Monitor participant until liver chemistry abnormalities resolve, stabilize, or return to within baseline values.
- Cases such as Gilbert syndrome, where baseline bilirubin values are high, should be discussed with the medical monitor, to assess if it is a case of drug-induced liver injury (DILI) or the participant may continue with dosing.

The procedures listed below are to be followed if a participant meets any of the liver chemistry stopping criteria defined in [Table 7](#):

Notify the Medical Monitor within 24 hours of learning of the abnormality to confirm the participant's study treatment cessation and follow-up.

Complete the Liver Event case report form (CRF).

Complete the "Safety Follow-up Procedures" listed below.

Safety Follow-up Procedures for Participants Who Meet Any of The Liver Monitoring and Stopping Criteria:

Viral hepatitis serology including:

- Hepatitis A IgM antibody;
- Cytomegalovirus IgM antibody;
- Epstein-Barr viral capsid antigen IgM antibody (or if unavailable, obtain heterophile antibody or monospot testing);
- Hepatitis E IgM antibody;
- Hepatitis B virus DNA load;
- Hepatitis C virus RNA load;
- Hepatitis D virus antibody.
- Obtain a blood sample for pharmacokinetic (PK) analysis as soon as possible following the occurrence of an event. Record the date/time of the PK blood sample collection and the date/time of the last dose of study treatment prior to blood sample collection on the CRF. If the date or time of the last dose is unclear, provide the participant's best approximation. Instructions for sample handling and shipping are included in the Study Reference Manual (SRM).
- Serum creatine phosphokinase (CPK) and lactate dehydrogenase (LDH).
- Review fractionated bilirubin
- Assess eosinophilia

- Record the appearance or worsening of clinical symptoms of hepatitis (fatigue, nausea, vomiting, right upper quadrant pain or tenderness, fever, rash or eosinophilia) as relevant on the Adverse Event (AE) CRF.
- Record use of concomitant medications, acetaminophen, herbal remedies, other over the counter medications, or putative hepatotoxins on the Concomitant Medications CRF.
- Record alcohol use on the Liver Events CRF.

The following are **required for participants who meet the ALT and bilirubin stopping criteria** but are optional for other abnormal liver chemistries.

- Anti-nuclear antibody, anti-smooth muscle antibody, Type 1 anti-liver kidney microsomal antibodies and quantitative total immunoglobulin G (IgG or gamma globulins).
- Serum acetaminophen adduct high performance liquid chromatography (HPLC) assay (quantifies potential acetaminophen contribution to liver injury in participants with definite or likely acetaminophen use in the preceding week [James, 2009]).
- Liver imaging (ultrasound, magnetic resonance, or computerized tomography) or Liver biopsy to evaluate liver disease.
- The Liver Imaging and/or Liver Biopsy CRFs are also to be completed if these tests are performed.

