10.5. Appendix 5: Genetics

USE/ANALYSIS OF DNA

- Genetic variation may impact a participant's response to study intervention, susceptibility, severity and progression of disease. Variable response to study intervention may be due to genetic determinants that impact drug absorption, distribution, metabolism, and excretion; mechanism of action of the drug; disease etiology; and/or molecular subtype of the disease being treated. Therefore, where local regulations and IRB/IEC allow, a blood sample will be collected for DNA analysis
- DNA samples will be used for research related to GSK3228836 or CHB and related diseases. They may also be used to develop tests/assays including diagnostic tests related to GSK3228836 or other 2'-MOE ASOs, and CHB. Genetic research may consist of the analysis of one or more candidate genes or the analysis of genetic markers throughout the genome or analysis of the entire genome (as appropriate)
- Additional analyses of DNA samples may be conducted if it is hypothesized that this may help further understand the clinical data.
- The samples may be analyzed as part of a multi-study assessment of genetic factors involved in the response to GSK3228836 or study interventions of this class. The results of genetic analyses may be reported in the clinical study report or in a separate study summary.
- The sponsor will store the DNA samples in a secure storage space with adequate measures to protect confidentiality.
- The samples will be retained while research on GSK3228836 (or study interventions of this class) or CHB continues but no longer than 15 years after the last participant last visit or other period as per local requirements.

10.6. Appendix 6: Liver Safety: Required Actions and Follow-up Assessments and Study Intervention Restart Guidelines

Phase 2 liver chemistry stopping and increased monitoring criteria have been designed to assure participant safety and evaluate liver event etiology.

The procedures listed below are to be followed if a participant meets any of the liver chemistry stopping criteria defined in Section 7.1.1.

If criteria for permanent discontinuation of IP are met, immediately withdraw the participant from study treatment.

Notify the Medical Monitor within 24 hours of learning of the abnormality to confirm the participant's study treatment cessation and follow-up.

Complete the Liver Event CRF.

Complete the "Safety Follow-up Procedures" listed below.

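### Protocol 7.1.1 gives two monitoring frequencies for a liver flare, and a Table 7 note makes optional a stop that row 4 and Appendix 6 make mandatory

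*Protocol*

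**What the plan says.** **Monitoring.** The body text of Protocol 7.1.1 states: "Participants must be monitored weekly until liver chemistry abnormalities (ALT, AST, alkaline phosphatase, bilirubin) resolve, stabilize, or return to within baseline values". Table 7, in the same section, sets a frequency row by row:

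- Row 1 (ALT 10x to below 12x ULN; bilirubin and INR not above 1.5x ULN and 1.5): "Monitor twice weekly Additional lab assessments". Dosing is not held.
- Rows 2 and 3 (ALT at least 12x ULN; or ALT at least 3x ULN with bilirubin above 1.5x and up to 2x ULN): "Hold dose Monitor twice weekly Additional lab assessments if not already done".
- Row 4 (ALT at least 3x ULN with bilirubin above 2x ULN, hepatitis symptoms, or INR above 1.5): "Permanently discontinue IMP Monitor twice weekly until stable ALT".

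**Stopping.** Section 7.1.1 opens by saying that study drug is to be stopped once the liver stopping criteria are met. Row 4 is a permanent stop. Appendix 6 (10.6) says: "If criteria for permanent discontinuation of IP are met, immediately withdraw the participant from study treatment". The note under Table 7 addresses any one listed criterion that has been met and confirmed by retesting, and says "further treatment may be discontinued for this participant after discussion with the Medical Monitor". It adds that the retest must be evaluated before the next dose.

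**The concern.** The protocol expects ALT flares in this population (2.3.1, Table 5), so sites will use this section.

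A site that follows the weekly sentence does half the routine checks that Table 7 asks for. This matters most in row 1, where dosing continues while ALT is 10 to 12 times the upper limit. A site that follows the note could treat a confirmed row 4 case as a matter for discussion. Row 4 includes combinations of ALT with bilirubin or INR that Appendix 2 (Table 11, note 3) describes as possible severe liver injury.

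At stake are participant safety and consistent handling across sites. The SAP (4.5.3.1) summarises liver monitoring and stopping events by reference to protocol 7.1.1, so the same section also defines what is reported.

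**Working it through.** The plan states no statistical figure on this point, so the check compares texts and counts visits.

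**1. Frequency.** Body text: once a week. Table 7: twice a week in rows 1, 2, 3 and 4, which is 4 of 4 rows. Rows 1 and 2 use a 4-week limit for a permanent stop, so 4 weeks is a natural window.

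- Weekly: 4 weeks x 1 = 4 routine checks.
- Twice weekly: 4 weeks x 2 = 8 routine checks.
- Ratio: 4 / 8 = 0.5.

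**2. One-off draws.** The repeat within 24 hours (7.1.1) and the confirmatory retest (7.1 and the Table 7 notes) apply whichever frequency is followed. The documents do not say whether they are one draw or two.

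- As 1 or 2 extra draws: 4 + 1 to 4 + 2 = 5 to 6, against 8 + 1 to 8 + 2 = 9 to 10. The difference is still 4.
- If the 24-hour repeat counts as one of the first week's two checks: 4 + 1 = 5 against 8. The difference is 3.

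**3. What weekly adds on treatment.** The Schedule of Activities has chemistry on Days 1, 8, 15, 22, 29, 36, 43, 50, 57, 64, 71 and 78. That is 12 draws, 7 days apart, or 4 per 28 days. For a participant still attending weekly, the weekly sentence therefore adds no routine draw to the existing schedule.

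**4. Do the two frequencies apply at different times?** The weekly sentence runs until the abnormalities resolve, stabilise or return to baseline. Row 4 runs until ALT is stable. Both can end at stabilisation, so the wording does not place weekly monitoring after a twice-weekly phase. Rows 1 to 3 give no end point for twice-weekly monitoring.

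**5. Stopping in row 4.** Three statements are mandatory: row 4 itself, the opening of 7.1.1, and Appendix 6. One is discretionary: the table note. The note applies after confirmation by retest, so its *may* is not merely a provision to wait for the retest. It excludes no row.

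**The case against.** **Weekly can be read as a floor.** A site checking twice weekly also satisfies a weekly rule, so both can be obeyed at once, and Table 7 is the more specific text. The weekly sentence names four analytes. The section also covers investigator-judged stops outside the Table 7 criteria. The restart rule in 7.1.5 already uses a step-down: twice a week until stable, then standard monitoring. Weekly is also a real increase for a participant on the reduced schedule after stopping (Weeks 3, 5 and 12 at minimum), or in follow-up, where visits are four-weekly after Week 16. This is a sensible reading and may be the intent. It stands as mitigation, but the text does not state it.

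**Row 4 is well protected.** The Medical Monitor must be told within 24 hours, and the stated purpose of that call is to confirm that treatment has ceased. Possible Hy's Law cases are SAEs, reportable within 24 hours (8.2.6.1, 10.3.2). No dose precedes evaluation of the retest. In the monitor and hold rows, *may* plausibly allows an earlier stop. All of this stands and makes a missed stop less likely. It does not remove the contradiction, and the Hy's Law rule does not name row 4's symptom limb.

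**Two stronger readings are tempting and not supported.**

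- "Discontinuation of study intervention for abnormal liver tests is required when" is followed by "a participant meets one of the conditions outlined in" Table 7. A reader might infer that the body text forces a stop in rows 1 to 3, which first monitor or hold. But Table 7 has a separate Discontinuation column, and 7.1.1 describes the table as covering both withholding and discontinuing. The sensible reading is that the conditions are those in that column.
- A reader might infer that immediate withdrawal in Appendix 6 contradicts retesting before withdrawal. It does not: criteria count as met once confirmed, withdrawal then follows at once, and no dose is given in between.

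**Conclusion.** Two conflicts hold in the current text: weekly against twice weekly, and a discretionary note against a mandatory row 4 stop. They should be corrected.

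The size of the first is 4 routine checks against 8, for a participant who stays four weeks within the Table 7 criteria, or a difference of 3 under the least favourable counting. The second concerns one word in a note, but it governs the most serious row.

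The documents do not say how many participants would reach a Table 7 row, so no number affected is claimed. The point assumes only that some sites may follow the body text or the note as written. It does not reach the primary endpoint, whose estimand disregards discontinuation and interruption of study drug.

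**What to change.** Make two changes to 7.1.1 by protocol amendment.

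(a) Replace the weekly sentence with: *Monitor participants at the Table 7 frequency (twice weekly) while a Table 7 criterion is met, and in row 4 until ALT is stable; thereafter at least weekly*, ending at the point the sentence already gives. This does not extend row 4's end point to rows 1 to 3.

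(b) Replace the table note with: *If a permanent-stop criterion in the Discontinuation column, including row 4, is met and confirmed by retest, study treatment will be permanently discontinued and the Medical Monitor notified. In the monitor and hold rows, treatment may be stopped earlier following discussion with the Medical Monitor. No dose is given until the retest result has been evaluated.* Keep the existing Gilbert syndrome note as the exception.

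Optionally, state that the Table 7 conditions requiring discontinuation are those in the Discontinuation column.

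The cost is a small amendment, with ethics approval under 10.1.1 and health authority approval if it is classed as substantial. A site letter alone is not the right vehicle for stopping language. The change adds no participants and no checks beyond those Table 7 and the weekly sentence already require.

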- Participants approved by GSK for restart of study intervention must return to the clinic twice a week for liver function tests until stable liver function tests have been demonstrated and then standard laboratory monitoring may resume as per protocol.
- If the participant meets protocol-defined liver chemistry stopping criteria after study intervention restart, study intervention should be permanently discontinued.
- The Medical Monitor and the IRB/IEC must be informed of the outcome for the participant following study intervention restart.
- GSK must be notified of any adverse events.

For treatment that has been placed on hold, please follow the guidelines above (Section 7.1.1 to Section 7.1.4).

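### Protocol Table 7: ALT ≥12x ULN loses its mandatory dose hold when bilirubin is >1.5x ULN but ≤35% direct, in a participant not already on hold, without hepatitis symptoms and with INR ≤1.5 or unavailable

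*Protocol*

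**What the plan says.** Table 7 is the protocol's list of criteria for withholding or stopping drug when ALT rises. Its four rows are:

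- **Row 1:** "10x ULN ≤ ALT <12x ULN and Bilirubin ≤1.5x ULN and INR ≤1.5 (if available". Monitor twice weekly, do additional laboratory tests, and stop permanently if ALT stays above 10x ULN for more than 4 weeks. There is no hold.
- **Row 2:** "ALT ≥12x ULN and Bilirubin≤1.5x ULN and INR ≤1.5 (if available". Hold the dose. The release rule is "Take off hold: 150 mg SC weekly when ALT <10x ULN".
- **Row 3:** "ALT ≥3x ULN and 1.5x ULN <bilirubin ≤2x ULN (>35% direct) and INR ≤1.5 (if available". Hold the dose. The release rule is "Take off hold: 150 mg SC weekly when bilirubin returns to <1.5x ULN".
- **Row 4:** ALT ≥3x ULN with any one of three triggers: "bilirubin >2x ULN (>35% direct"), new or worsening hepatitis symptoms, or INR >1.5 if available. Stop permanently.

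The notes under the table say that clinically significant deterioration "must be confirmed by retesting ALT, total bilirubin, direct bilirubin, and INR (if available"). They also send cases such as Gilbert syndrome with high baseline bilirubin to the Medical Monitor. Notification of the Medical Monitor within 24 hours, the Liver Event CRF and the safety follow-up procedures are all tied to meeting the table's criteria.

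**The concern.** Rows 1 and 2 stop applying once bilirubin passes 1.5x ULN. The rows meant to take over above that level require a direct fraction above 35%. A participant whose raised bilirubin is mainly indirect falls between them. The direct-fraction condition sensibly keeps benign indirect hyperbilirubinaemia from making a liver event look worse. It gives no reason for indirect bilirubin to cancel a hold that ALT alone would trigger.

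At stake is whether the next dose is withheld by rule or by judgement during a marked flare. Table 5 expects ALT flares in this population, and Table 6 anticipates their start around Week 5, while dosing runs to Day 78. Sites could handle the same ALT differently, and the notification, CRF and work-up tied to Table 7 would not be mandated.

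**Working it through.** The plan states no figure to reproduce, so the check is one of logic.

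**1. The rows as conditions.** Values are multiples of ULN; d is the percentage direct. I15 means INR ≤1.5 or unavailable.

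- Row 1: 10 ≤ ALT < 12, bilirubin ≤1.5, I15
- Row 2: ALT ≥12, bilirubin ≤1.5, I15
- Row 3: ALT ≥3, 1.5 < bilirubin ≤2, d >35, I15
- Row 4: ALT ≥3 and (bilirubin >2 with d >35, or symptoms, or INR >1.5)

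**2. Single samples, I15, no symptoms.**

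| ALT | Bilirubin | Direct | Row met | Consequence |
|---|---|---|---|---|
| 15x | 1.5x | 30% | 2 | Hold |
| 15x | 1.6x | 30% | none | none mandated |
| 15x | 1.8x | 30% | none | none mandated |
| 15x | 2.5x | 30% | none | none mandated |
| 15x | 1.8x | 40% | 3 | Hold |
| 11x | 1.2x | 30% | 1 | Twice-weekly monitoring, 4-week stop |
| 11x | 1.8x | 30% | none | none mandated |

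**3. Grid.** ALT {10, 11, 12, 13, 15, 20} × bilirubin {1.0, 1.25, 1.5, 1.6, 1.8, 2.0, 2.5, 3.0} × direct {20, 30, 35, 36, 40, 50}% gives 6 × 8 × 6 = 288 points. With no symptoms and INR unavailable or 1.2, the points meeting no row are exactly those with bilirubin >1.5x and ≤35% direct: 6 × 5 × 3 = 90. Of these, 4 × 5 × 3 = 60 have ALT ≥12x and 2 × 5 × 3 = 30 have ALT 10 to <12x. With INR 1.6 or symptoms, all 288 fall in row 4. These counts test the logic and say nothing about frequency.

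**4. Courses over time (ALT, bilirubin, % direct).**

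- (15, 1.2, 30) then (15, 1.8, 30): the row 2 hold continues, since only ALT <10x releases it. No gap.
- (15, 1.8, 40) then (15, 1.8, 30): the row 3 hold continues, since only bilirubin <1.5x releases it. No gap.
- (8, 1.8, 30) then (15, 1.8, 30): no row, no hold.
- (5, 1.2, 30) then (15, 1.6, 30): no row, no hold.
- (11, 1.2, 30) then (15, 1.8, 30): row 1, then no row.

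Protocol 7.1.5 supports the first two: "For treatment that has been placed on hold, please follow the guidelines above". The gap therefore opens only if bilirubin is already above 1.5x ULN, or crosses it in the same sample, when ALT first reaches the threshold.

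**5. Can a participant get there?** Exclusion criterion 18 admits bilirubin up to 1.25x ULN without discussion, so a rise of more than 1.5 − 1.25 = 0.25x ULN passes the cap. Benign unconjugated hyperbilirubinaemia above 1.25x can be admitted after discussion with the Medical Monitor.

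**6. Scheduled INR.** In Tables 2 and 3, chemistry is scheduled at 11 dosing visits on Days 8 to 78 (8, 15, 22, 29, 36, 43, 50, 57, 64, 71, 78) and INR at 3 of them (15, 29, 57). From Day 29 the figures are 8 and 2.

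**The case against.** The best defence is that other provisions catch these participants. Clinically significant deterioration must be retested, and a rise to 12x ULN in someone admitted at ≤2x ULN would plainly qualify. A further note requires retest results to be evaluated before the next dose. Gilbert-type cases with high baseline bilirubin go to the Medical Monitor, the investigator may stop drug even when no rule is met, and an internal Safety Review Team reviews all safety data (protocol 10.1.5).

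Much of this stands, and it lowers the severity. It does not close the gap. The note about evaluating retests before dosing sits in a bullet about a criterion already met, so its reach here is arguable; even read broadly, it delays dosing only until review. The Gilbert note concerns high baseline values and does not clearly cover a normal baseline that rises to 1.6x. The rest is discretionary. None of these provisions sets a mandatory hold with a release threshold.

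Several stronger readings are tempting but unsupported:

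- *A hold is also lost at ALT 10 to <12x.* Row 1 has no hold at any bilirubin level.
- *Any indirect bilirubin rise at this ALT escapes the table.* With symptoms or INR >1.5, row 4 requires permanent discontinuation.
- *INR cover is only as good as the schedule.* The retest note adds INR where available, so the 3-of-11 count understates cover in this situation.
- *These participants vanish from safety reporting.* They might not be counted as Table 7 events, but SAP 4.5.3.1 still summarises hepatobiliary abnormalities and increases to Grade 3 or higher, and SAP 4.5.2.1 reports ALT increase as an event of special interest.
- *Row 3's release rule is also defective because it ignores ALT.* It allows 150 mg weekly at ALT 10 to <12x, but row 1 allows dosing to continue at that ALT with no hold, and row 2 applies again at ≥12x. Changing it would be a preference.

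**Conclusion.** Table 7 is wrong as written, with low-to-moderate severity. At ALT ≥12x ULN, a higher bilirubin can remove a mandatory hold. At ALT 10 to <12x it removes twice-weekly monitoring, additional tests and the 4-week permanent stop. The Table 7 notification, CRF and follow-up work-up also cease to be mandated.

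This depends on five conditions holding together: no hold in force, bilirubin >1.5x ULN, ≤35% direct, INR ≤1.5 or unavailable, and no new or worsening hepatitis symptoms. The documents give no rate for the combination, so no probability is stated; in 20 to 24 participants it is probably low. A reader might infer that the efficacy result is at risk. It is not: the primary estimand ignores interruption and discontinuation of drug. The point concerns participant safety and consistency between sites.

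**What to change.** In rows 1 and 2 of Table 7, replace the bilirubin condition with: *bilirubin ≤1.5x ULN, or >1.5x ULN with ≤35% direct*. State that row 4 takes precedence, and keep the Medical Monitor discussion for Gilbert-type cases. Leave row 3 unchanged.

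On the grid above, 60 of the 90 uncovered points move to row 2 and 30 to row 1. The other 288 − 90 = 198 keep their row, and none is left without one.

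The cost is a one-table protocol amendment, which needs ethics approval and, if substantial, health authority approval (protocol 10.1.1); it can be bundled with another amendment. Participants with indirect hyperbilirubinaemia would have a few more held doses and twice-weekly checks. No new type of visit or test is needed, and the SAP needs no edit because its section 4.5.3.1 refers to protocol 7.1.1.
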